5.1 Method of Assigning Patients to Treatment Groups

Patients will be randomly assigned to receive riociguat or placebo using a 1:1 allocation ratio. An interactive web response system (IWRS) will be used to administer the randomisation schedule. Biostatistics will generate the randomisation schedule using SAS® software Version 9.3 or later (SAS Institute Inc, Cary, North Carolina) for IWRS, which will link sequential patient randomisation numbers to treatment codes. It will also use an appropriate block size, which will not be revealed.

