3.1 Study Design

This is a randomised, double-blind, placebo-controlled, multicentre, multinational, prospective study in patients with operable CTEPH prior to PEA with high preoperative PVR ($>800 \text{ dyn}\cdot\text{s}\cdot\text{cm}^{-5}$). Eligible patients will be randomly assigned to riociguat or matching placebo tid in a 1:1 ratio. A total of 88 patients are planned to randomly assign at 4 sites in North America and Europe.

A schematic of the study design is presented in Figure 3-1.

Figure 3-1

Study Schematic

Abbreviations: PEA, pulmonary endarterectomy; RHC, right heart catheterisation; V, visit

Patients will undergo a screening period of up to 89 days prior to baseline (Visit 1). Following completion of the pretreatment screening phase, eligible study patients will be randomly assigned into the study.

The study will comprise 3 study periods:

- **Screening Period (Day -89 to Day 1):** The screening period of up to 90 days will be used to assess eligibility of patients and to allow for the washout of prohibited medications. Screening visit (V0) and randomisation visit (V1) can occur on the same day.
- **Treatment Period (Day 1 [Baseline] through Day 90):** Patients will be randomly assigned on Day 1 to receive either riociguat or matching placebo tid in a 1:1 ratio for 3 months. The study drug will be initiated at 1 mg and the dosage can be increased by 0.5 mg at 2-week intervals based on tolerability (SBP) up to a maximum dose of 2.5 mg tid based on the algorithm mentioned in Section 5.2. The study drug will be initiated no later than 180 days after right heart catheterisation (RHC) (used for screening of patients) and within 90 days of planned RHC before PEA. At Visit 2, RHC will be performed per site procedures no more than 1 week prior to PEA, which will be conducted by the principal surgeon of the site. The study drug will be discontinued once PEA is performed. The last study dose will be given on the morning of PEA surgery. The patient will remain hospitalised per the investigator's discretion.
- **Follow-up Period:** A follow-up visit is planned at 6 months after PEA, at which time RHC will also be performed per study site procedures.

A telephonic call visit is planned during treatment period and at Day 186±10 during follow-up period, where treating physician or designee will call patient to ask questions related to patient's well-being and any adverse events.

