3.4. Dose Adjustment/Modifications

The study drug will be initiated at 1 mg and the dosage can be increased by 0.5 mg at 2-week intervals based on tolerability (SBP) up to a maximum dose of 2.5 mg tid. The individual study drug dose of the next titration step will be determined every 2 weeks at home according to the peripheral SBP measured at trough before intake of the morning dose under consideration of the following algorithm:

- If trough SBP \geq 95 mmHg, increase dose (+0.5 mg tid)
- If trough SBP <95 mmHg without symptoms of hypotension, maintain dose
- If any SBP <95 mmHg with clinical symptoms of hypotension such as dizziness or presyncope, stop study drug; restart after 24 hours with reduced dose (-0.5 mg tid)

The blood pressure (BP) measuring device will be supplied along with study drug to each patient to monitor BP at home. If the dose is interrupted for 3 or more days, restart the dose with 1 mg tid and follow the up-titration algorithm. The up titration will be monitored by study staff contacting the patient by telephone at home.

4. General Statistical Considerations

- Data from all study centers will be combined for analysis.
- Statistical methods to be used will be mainly descriptive. Summary statistics will be tabulated and represented graphically, whenever appropriate.
- Continuous data will be summarised using descriptive statistics (i.e. n, mean, standard deviation, median, minimum, and maximum). Besides presentation of absolute values, tabulation for differences to baseline by time will be provided, if appropriate. Categorical data will be summarised using the frequency counts and percentages. Time to event data will be analysed using the Kaplan-Meier method.

- For the summary statistics of all numerical variables, unless otherwise specified, minimum and maximum will be displayed to the same level of precision as reported. Mean and median will be displayed to one level of precision greater than the data collected. Standard deviation / standard error will be displayed to two levels of precision greater than the data collected. P-values will be rounded to three decimal places. If a p-value is less than 0.001 it will be reported as “<0.001”. If a p-value is greater than 0.999 it will be reported as “>0.999”.

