4.2. Randomisation, Stratification, and Blinding

Following completion of the screening period, eligible study patients will be randomly assigned into the study. An interactive web response system (IWRS) will be used to administer the randomisation schedule. In order to obtain a treatment group assignment for a patient, a site representative will access the IWRS. Patients will be randomly assigned on Day 1 to receive

either riociguat or matching placebo tid in a 1:1 allocation ratio for 3 months. No stratification of the randomisation schedule will be performed.

The clinical study will be performed in a double-blinded manner. The investigator, study coordinator(s), patients, and the sponsor study team and its representatives will be blinded to the identity of the randomised treatment assignment from the time of randomisation until database lock. Randomisation data will be kept in strict confidence by the statistician who will generate the randomisation schedule, the IWRS provider, and the vendor involved in the study drug labelling. The identity of the treatments will be concealed by the use of study drugs that are all identical in packaging, labelling, schedule of administration, appearance, taste, and odour.

A patient's treatment assignment will not be broken until the end of the study unless medical treatment of the patient depends on knowing the study drug the patient received. In the event that the blind needs to be broken because of a medical emergency, the investigator may unblind an individual patient's treatment allocation. As soon as possible, the investigator should first contact the medical monitor to discuss the medical emergency and the reason for revealing the actual treatment received by that patient. The treatment assignment will be unblinded through IWRS. Reasons for treatment unblinding must be clearly explained and justified in the eCRF. The date on which the code was broken together with the identity of the person responsible must also be documented.

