8.2.3. Perioperative Findings

8.2.3.1. Circulatory Arrest Time

Circulatory arrest time (minute) at Visit 2 from perioperative findings will be tabulated by treatment group using the descriptive statistics for the PEA set. An analysis of variance (ANOVA) will be employed to compare the mean difference between 2 groups. P-value from Shapiro-Wilk test will also be presented in this table to indicate the normality of this variable. In case normality assumption cannot hold, the Wilcoxon rank-sum test should be considered.

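### Neither the randomisation nor any planned test uses site, although site and surgeon are one factor; adding site is a cheap gain in precision, mainly for the surgeon-dependent endpoints

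*Protocol*

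**What the plan says.** **Allocation.** Protocol 3.1: "A total of 88 patients are planned to randomly assign at 4 sites in North America and Europe". Protocol 5.1 describes a single 1:1 schedule run through the IWRS, which "will link sequential patient randomisation numbers to treatment codes. It will also use an appropriate block size, which will not be revealed"; it names no stratification factor. That section only implies an unstratified list. SAP 4.2 is explicit: "No stratification of the randomisation schedule will be performed".

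**What differs by site.** Under Protocol 3.1 the Visit 2 catheterisation is done "per site procedures no more than 1 week prior to PEA, which will be conducted by the principal surgeon of the site". Site, surgeon and local catheter practice therefore coincide.

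**Analysis.** Protocol 7.8 leaves covariates to the SAP. SAP section 4 says: "Data from all study centers will be combined for analysis". The only covariate the SAP then names is baseline PVR, in the supportive ANCOVA (SAP 8.1). None of the following has a site term or stratum:
- the Wilcoxon tests on PVR (SAP 8.1, 8.2.1)
- the Fisher tests (SAP 8.2.2, 8.2.3.2)
- the circulatory arrest time analysis, "An analysis of variance (ANOVA) will be employed to compare the mean difference between 2 groups" (SAP 8.2.3.1)
- the Cochran-Mantel-Haenszel tests of the specimen scores (SAP 8.2.4)
- the Hodges-Lehmann estimates (SAP 8.3)

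No by-site table is planned.

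**The concern.** Blocking the overall sequence balances the arms in total but not within a site. Several endpoints plausibly depend on who operates and where: circulatory arrest time, complications, ventilation time, and ICU and hospital stay. The specimen scores depend on it by construction, because dissection, clearance and friability are each graded against what the rater regards as normal, expected or usual (Protocol 6.2.8).

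If one surgeon happens to operate on more patients of one arm, part of that surgeon's habit appears as an arm difference. Even without a marked imbalance, variation between sites stays in the error term. Effects during PEA are a stated secondary objective (Protocol 2.2), so a reader of those tables will want to know whether a difference is drug or surgeon.

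**Working it through.** **Inputs from the documents.** 88 randomised, 4 sites, 1:1, no stratification; 80 completers targeted (Protocol 4.3.3), taken as 40 per arm; two-sided 5% tests.

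**Assumed, because the documents give no value.** Block size 4; 22 patients per site; a true difference of 0.6 SD; site share of outcome variance *s* from 0 to 0.3.

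**Plan's own figure.** 80 × 1.10 = 88 reproduces the planned number (80/0.90 would give 89). Protocol 7.5 says the size rests on feasibility, so there is no power figure to reproduce.

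**Step 1: imbalance within a site.** At a site of 22 the number on riociguat has mean 11 and SD √(22 × ¼ × 66/87) = 2.04. A split of 14:8 or worse is a deviation of at least 3, with probability about 2 × [1 − Φ(2.5/2.04)] = 0.22 at any one site. The four counts must sum to 44, so the chance for at least one site was simulated:

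| Unstratified list, blocks of 4 | Chance |
|---|---|
| Sites of 22, some site 14:8 or worse | about 55% |
| Sites of 22, some site 15:7 or worse | about 26% |
| Sites of 40/24/16/8, arm difference of 6 or more at some site | about 49% |

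With permuted blocks within site, a difference of 6 or more did not occur.

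**Step 2: what an imbalance does.** If one surgeon's mean differs from the others' common mean by D, a 14:8 split at that site shifts the pooled comparison by D × (14 − 8)/44 = 0.14 D; a 15:7 split shifts it by 8/44 = 0.18 D. The direction is random.

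**Step 3: type I error.** The simulated pooled Wilcoxon test on an unstratified list rejected in 4.6% to 5.1% of null trials for every *s* from 0 to 0.3.

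**Step 4: power from adding site to a linear model, list left unstratified.** Power ≈ Φ(0.6 × √(n/2)/σ − 1.96).
- Pooled: n = 40 and σ² = 1 − s/4, because with four sites drawn at random the realised between-site variance averages ¾ s.
- Adjusted: σ² = 1 − s. Site explains on average 3.5% of the allocation under an unstratified list, so n = 40 × 0.965 = 38.6.

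| s | Pooled | Site in model | Difference in points |
|---|---|---|---|
| 0 | 76.5% | 75.0% | −1.5 |
| 0.05 | 77.0% | 77.2% | about 0 |
| 0.10 | 77.6% | 79.3% | about +2 |
| 0.20 | 78.6% | 83.8% | about +5 |
| 0.30 | 79.7% | 88.3% | about +8.6 |

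Direct simulation gives about +2, +5 and +7 to 8 at the last three shares. The formula is slightly generous at 0.30 because it treats the realised site variance as fixed.

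**Step 5: the rank test.** The rank-based counterpart is the van Elteren test. Simulated power, Wilcoxon versus van Elteren, on the same unstratified list of 80:

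| s | Equal sites | Sites in 40/30/20/10 proportion |
|---|---|---|
| 0 | 72.0 vs 68.8% | 73.4 vs 69.4% |
| 0.05 | 72.9 vs 70.4% | 74.9 vs 73.6% |
| 0.10 | 75.0 vs 75.1% | 74.2 vs 74.2% |
| 0.20 | 76.3 vs 80.7% | 76.6 vs 79.2% |
| 0.30 | 76.4 vs 84.2% | 76.9 vs 83.8% |

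The stratified rank test loses about 1 to 4 points at a share of 5% or less, breaks even at 10% and gains only above that.

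**The case against.** The other side has four good arguments.

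- **Validity.** A reader might infer that the unstratified list biases the comparison or inflates type I error. It does neither (step 3). The SAP states the choice openly, all analyses are declared exploratory (Protocol section 7), and unstratified allocation is harder to predict within a site. This stands and limits the severity.
- **Separability.** A reader might infer that a realised imbalance cannot be told apart from a drug effect. That is wrong: site is known for every patient, and a 14:8 or 15:7 site still has both arms, so a site term separates the two. What remains is that no such analysis is planned.
- **PVR.** The primary endpoint is a percent change within patient, so a constant proportional site effect cancels when both catheterisations follow the same practice. Protocol 6.2.11 also asks for one cardiac output method per patient. Cancellation can fail when the baseline reading came from a referring centre, which Protocol 3.1 allows, but the trial-site stratum does not identify that source either. PVR is the weakest case, and the documents do not support replacing the primary Wilcoxon test by a stratified one. This stands in full.
- **Size.** The gain depends on a site share that the documents do not give, and Protocol 4.1 describes all four sites as high-volume and experienced. This stands: the larger gains need a share of 20% to 30%.

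None of this answers the omission for circulatory arrest time and the surgeon-rated scores, where a site effect is most plausible and the remedy is a model term or a stratum.

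**Conclusion.** The point holds as a cheap improvement, strongest for surgeon-dependent endpoints. With 22 patients per site and blocks of 4, a split of 14:8 or worse under at least one surgeon is slightly more likely than not. Such a split moves the pooled comparison by about 14% of that surgeon's difference from the others, in a random direction. The consequence is lost precision and an unanswered question of interpretation, not invalid tests.

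The benefit of a site term is nil at a site share of 5% or less and reaches 7 to 8 power points at 30%, for a continuous endpoint with a 0.6 SD difference and 80 completers. The cost if site explains nothing is 1 to 2 points. Block size, site split, effect size and site share are all assumptions.

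**What to change.** **IWRS.** For patients not yet randomised, use permuted blocks within each of the four sites. The documents do not show how many patients that would be; if none, the SAP changes are valid on their own. The cost is a schedule set-up and slightly more predictable allocation within a site, which is minor under double blinding with an undisclosed block size.

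**SAP, before unblinding.**
- Add site as a factor to the circulatory arrest time ANOVA (8.2.3.1) and to the supportive ANCOVA (8.1).
- Stratify the Cochran-Mantel-Haenszel tests of the specimen scores by site (8.2.4).
- Keep the Wilcoxon test as the primary PVR analysis, and add a van Elteren test stratified by site as a sensitivity analysis only.
- Tabulate arm by site.

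The cost is a few lines and 3 degrees of freedom. If the list is stratified while the primary test stays pooled, that test becomes mildly conservative: simulated type I error was 4.9% with no site effect and 3.1% at a 30% share. Power was 72.4% and 80.0%, against 73.4% and 76.9% on the unstratified list, so nothing material is lost.

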5.2 Treatments Administered

Patients will initiate the treatment with either riociguat or matching placebo tablets orally tid for 3 months. The study drug will be initiated no later than 180 days after RHC (used for screening of patients) and within 90 days of planned RHC before PEA. Right heart catheterisation will be performed within 3 months of the initiation of treatment per site procedures no more than 1 week prior to PEA. The study drug will be initiated at 1 mg and the dosage can be increased by 0.5 mg at 2-week intervals based on tolerability (SBP) up to a maximum dose of 2.5 mg tid. The individual study drug dose of the next titration step will be determined every 2 weeks at home according to the peripheral SBP measured at trough before intake of the morning dose under consideration of the following algorithm:

- If trough SBP \geq 95 mmHg, increase dose (+0.5 mg tid)
- If trough SBP $<$ 95 mmHg without symptoms of hypotension, maintain dose
- If any SBP $<$ 95 mmHg with clinical symptoms of hypotension such as dizziness or presyncope, stop study drug; restart after 24 hours with reduced dose (-0.5 mg tid)

The BP measuring device will be supplied along with study drug to each patient to monitor BP at home. If the dose is interrupted for 3 or more days, restart the dose with 1 mg tid and follow the up-titration algorithm. The up titration will be monitored by study staff contacting the patient by telephone at home.

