4.1.2 Exclusion Criteria

Patients meeting any of the following criteria will be excluded from the study:

1. Has unstable disease in need of urgent PEA surgery as determined by the treating physician
2. Has known hypersensitivity, allergic, or adverse reactions to riociguat or any of the excipients comprising riociguat tablets
3. Has known active hepatitis A immunoglobulin M, hepatitis B surface antigen, or hepatitis C antibody
4. Is human immunodeficiency virus positive
5. Has pulmonary veno-occlusive disease
6. Has symptomatic hypotension
7. Has symptomatic carotid disease
8. Has significant coronary atherosclerotic disease in need of intervention
9. Has severe left heart disease in need of intervention
10. Has redo sternotomy
11. Has received any background therapy for PAH in the preceding 30 days before Visit 1 including ERAs, PDE5 inhibitors, or prostanooids
12. Is receiving nitrates, NO donors (eg, amyl nitrite), ERAs, prostanooids, specific PDE5 inhibitors, nonspecific phosphodiesterase inhibitors (eg, dipyridamole, theophylline)
13. Is receiving strong cytochrome P450 and P-glycoprotein/breast cancer resistance protein inhibitors
14. Is receiving strong cytochrome P450 3A inducers
15. Has creatinine clearance <15 mL/min or is on any form of dialysis
16. Has severe hepatic impairment classified as Child-Pugh B or C

17. Has received an investigational drug within the past 4 weeks before Visit 1
18. Is a lactating or pregnant (as demonstrated by a serum or urine dipstick pregnancy test) woman, or not willing to take measures not to become pregnant during the 3-month treatment study period and 1 month after the last dose of study drug administered
19. Has smoked or used tobacco in any form, including snuff or chewing within 3 months prior to Visit 1
20. Has idiopathic interstitial pneumonitis

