4.3.1 Reasons for Withdrawal/Discontinuation

Patients may withdraw from the study at any time and for any reason without prejudice to their future medical care by the investigator or at the study site. Every effort should be made to keep patients in the study. The reasons for patients not completing the study will be recorded. A patient may be withdrawn from the study for any of the following reasons:

1. Does not meet the protocol inclusion or exclusion criteria
2. Noncompliance with the protocol
3. A serious or intolerable AE that in the investigator's opinion requires withdrawal from the study
4. Laboratory safety assessments that reveal clinically significant haematological or biochemical changes from the baseline values
5. Symptoms or an intercurrent illness not consistent with the protocol requirements or that justifies withdrawal
6. Loss to follow-up
7. Other (eg, pregnancy, development of contraindications of use of study drug)
8. If the investigator believes that continued administration of the study drug is contrary to the best interests of the patient
9. The patient withdraws consent or the investigator or sponsor decides to discontinue the patient's participation in the study

The investigator will also withdraw a patient if International CTEPH Association (ICA) terminates the study. Upon occurrence of a serious or intolerable AE, the investigator will confer with the sponsor. If a patient is discontinued because of an AE, the event will be followed until it is resolved. Any patient may withdraw his or her consent at any time.

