5.3 Identity of Investigational Product

Riociguat is a film-coated, round shaped with 6-mm diameter, immediate-release tablet of pale orange colour. The excipients include lactose, microcrystalline cellulose, crospovidone, magnesium stearate, hypromellose, and sodium lauryl sulfate.

Placebo tablets are identical in appearance to riociguat but do not have the active compound. The excipients include lactose, microcrystalline cellulose, crospovidone, magnesium stearate, hypromellose, and sodium lauryl sulfate.

Study drug will be provided by the drug manufacturer to PPD (designated contract research organisation) for further distribution to sites.

The following drug supplies will be used in the study:

Product	Supplied as
Riociguat	0.5 mg, 1 mg, 1.5 mg, 2 mg and 2.5 mg tablets
Placebo	Matching tablets

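### After 3 or more days off drug, the restart rule puts a patient reduced to 0.5 mg tid for hypotension back on 1 mg tid, without the 2-week point or SBP condition

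*Protocol*

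**What the plan says.** Protocol 5.2 starts study drug at 1 mg tid and allows 0.5 mg steps up to 2.5 mg tid. The "dose of the next titration step will be determined every 2 weeks at home according to the peripheral SBP measured at trough". Three algorithm rules follow:

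- Trough SBP at or above the threshold: "95 mmHg, increase dose (+0.5 mg tid".
- Trough SBP below "95 mmHg without symptoms of hypotension, maintain dose".
- Any SBP below 95 mmHg with symptoms such as dizziness or presyncope: "stop study drug; restart after 24 hours with reduced dose (-0.5 mg tid".

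A separate sentence covers longer gaps: "If the dose is interrupted for 3 or more days, restart the dose with 1 mg tid and follow the up-titration algorithm". It names no exception for the dose held before the gap or for the cause of the gap, and it attaches no SBP condition to the restart dose. The synopsis and SAP 3.4 carry the same text. Protocol 5.3 lists "0.5 mg, 1 mg, 1.5 mg, 2 mg and 2.5 mg tablets", so 0.5 mg tid is a usable dose level.

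**The concern.** For patients above 1 mg tid, the gap rule is protective because it lowers the dose. At 0.5 mg tid it raises the dose. Dosing begins at 1 mg and comes down only under the symptomatic-hypotension rule, so every patient on 0.5 mg has already had symptomatic hypotension at 1 mg. A gap of 3 days for any reason then returns that patient to 1 mg by default.

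A second problem arises one level up. A patient stopped for symptoms at 1 mg should resume at 0.5 mg. If the stop lasts 3 days or more, the gap rule instead gives back the dose at which symptoms occurred, and nothing says which rule governs.

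Patient safety is what is at stake. Protocol 6.3.1.7 lists hypotension and syncope as adverse events of special interest. Titration is decided at home, and the schedule of events has no site visit between Visit 1 and Visit 2, so the written rule carries much of the weight.

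**Working it through.** The plan gives no figure to reproduce. The check applies each rule to each supplied strength.

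Inputs (Protocol 5.2 and 5.3): strengths 0.5, 1, 1.5, 2 and 2.5 mg; hypotension rule = prior dose − 0.5 mg; gap rule = 1 mg. The proposed restart is min(1.0, dose otherwise due), with a floor of 0.5 mg. The dose otherwise due is the prior dose, or the prior dose − 0.5 mg after symptoms. All doses are mg tid.

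| Prior dose | Symptom stop: hypotension rule | Symptom stop, 3+ days: gap rule | Other stop, 3+ days: gap rule | Proposed, symptom stop | Proposed, other stop |
|---|---|---|---|---|---|
| 0.5 | 0.5 − 0.5 = 0, no dose defined | **1.0** | **1.0** | investigator: 0.5 or discontinue | 0.5 |
| 1.0 | 0.5 | **1.0** | 1.0 | 0.5 | 1.0 |
| 1.5 | 1.0 | 1.0 | 1.0 | 1.0 | 1.0 |
| 2.0 | 1.5 | 1.0 | 1.0 | 1.0 | 1.0 |
| 2.5 | 2.0 | 1.0 | 1.0 | 1.0 | 1.0 |

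**Count.** 5 strengths × 2 reasons = 10 cells. Three are affected (bold): other stop at 0.5 mg, symptom stop at 0.5 mg, symptom stop at 1 mg. 10 − 3 = 7 stay at 1.0 mg tid. At 1.5 mg the two rules agree. At 2.0 and 2.5 mg they differ, but the gap rule gives the lower dose.

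**Dose change at 0.5 mg.** 3 × 0.5 = 1.5 mg/day becomes 3 × 1.0 = 3.0 mg/day, a doubling.

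**Timing.** Assume the 2-week interval runs from the reduction; the documents do not say. Take Day 1 on 0.5 mg and Days 2 to 4 off drug. The gap rule then gives 1 mg on Day 5. The ordinary step falls on Day 1 + 14 = Day 15, so the return is 15 − 5 = 10 days early. This is an illustration, not a bound. A later gap shortens the difference. A trough SBP that stays below 95 mmHg without symptoms means the dose is held, so the ordinary return may come after Day 15 or never.

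**Patients.** The documents give no number for these sequences. Planned riociguat patients are 88/2 = 44. The hypotension rates in Protocol 1.4 would give 44 × 11/75 = 6.5 (Study 12166, PAH or CTEPH) and 44 × 0.119 = 5.2 (Study 14308, 2.0 mg group). These count hypotension at any dose in other populations, and some symptoms here may be coded as dizziness. The affected cells also need symptoms at 1 mg and a stop of 3 or more days.

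**Cost of a lower restart.** From 1 mg to 2.5 mg: (2.5 − 1.0)/0.5 = 3 steps = 42 days. From 0.5 mg: (2.5 − 0.5)/0.5 = 4 steps = 56 days. With treatment through Day 90 and no further interruption, the latest restart that still reaches 2.5 mg is Day 90 − 56 = 34 from 0.5 mg and Day 90 − 42 = 48 from 1 mg.

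**The case against.** The strongest answer is that this is a rare corner with other protection around it.

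- A symptom stop is meant to end after 24 hours. Followed that way, it never meets the gap rule. This stands: a reader might infer that the two rules always clash at 1 mg, but the text does not support that. The clash needs a stop that reaches 3 days. That can happen, because the 24-hour wording sets no upper limit.
- A return to 1 mg is already planned. This also stands, but the algorithm makes it depend on a 2-week point and a trough SBP of at least 95 mmHg. Its instruction to follow the algorithm governs the steps after the restart; the restart dose itself is already fixed at 1 mg.
- First dosing at 1 mg has no SBP threshold either. True, but exclusion criterion 6 ("Has symptomatic hypotension") keeps affected patients out at entry. A patient on 0.5 mg has since developed the condition at 1 mg.
- Safeguards exist: the symptom stop rule applies again, patients have home BP devices and telephone monitoring, Protocol 4.3.1 permits withdrawal ("If the investigator believes that continued administration of the study drug is contrary to the best interests of the patient"), and Protocol 10.2.2 allows deviations for an immediate hazard. These lower the risk. None of them changes the written restart dose.
- A separate amendment needs ethics and regulatory approval (Protocol 10.2.1), which is heavy for possibly no patients. This stands and shapes the fix.

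**Conclusion.** The concern holds as a minor patient-safety correction. In 3 of 10 dose-by-reason cells, the written rule either returns a patient to a dose that caused symptomatic hypotension, outside the algorithm's own conditions, or leaves two rules giving different doses. The 0.5 mg finding needs no numerical assumption. The 10-day illustration rests on the 2-week clock starting at the reduction.

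Three stronger readings are not supported. The rates of 5.2 to 6.5 per 44 do not size the problem; few patients, possibly none, would meet it. The gap rule is not unsafe in general, since above 1 mg it never raises the dose. Nothing in the documents shows an effect on the primary endpoint, the sample size or the error rate, and none is claimed.

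**What to change.** Replace the restart sentence in Protocol 5.2, and make the same edit in the synopsis and SAP 3.4:

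> After an interruption of 3 or more days, restart at 1 mg tid or at the dose otherwise due (the prior dose, or the reduced dose after symptomatic hypotension), whichever is lower but not below 0.5 mg tid, then continue with the titration algorithm. After symptomatic hypotension at 0.5 mg tid, the investigator decides whether to resume at 0.5 mg tid or discontinue.

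The cap settles precedence at 1 mg. The floor and the last sentence prevent a restart dose of zero. No separate SBP check is needed, because a patient restarted at 0.5 mg reaches 1 mg only through the algorithm's own 2-week and SBP conditions.

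Bundle the edit with the next amendment. It adds no procedure or patient, and the 0.5 mg strength is already supplied. The downside is that a few patients restart one 0.5 mg step lower and need 8 weeks instead of 6 to reach 2.5 mg tid. On the Day 90 assumption, a restart on Days 35 to 48 would reach 2.5 mg only from 1 mg; the dose at Visit 2 would be at most one step lower.
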